### **3.2 Experience with the use of dupilumab in COVID-19**

Dupilumab, an anti-interleukin-4 receptor- $\alpha$  monoclonal antibody, leading to blockage of IL-4 and IL-13 signaling, has been FDA approved for treatment of moderate to severe atopic dermatitis since 2017. It has been successfully shown to reduce disease severity in not only those with atopic dermatitis but in other allergic diseases where Th2 cytokines have been implicated, including asthma and chronic rhinosinusitis. Original clinical trials noted excellent safety profiles in addition to favorability in its use when considering the negative impacts of long term steroid use in these patients.

We have previously conducted a phase IIa randomized double-blind placebo-controlled trial to assess the safety and efficacy of dupilumab plus standard of care versus placebo plus standard of care in mitigating respiratory failure and death in those hospitalized with COVID-19. Subjects were followed prospectively for 60 days, with collection of clinical outcomes, adverse events and immunologic biomarkers at multiple time points throughout the study period. Through this trial we found that dupilumab was safe to use for this indication, that there was reduced 60-day mortality in those who received dupilumab compared to placebo and that there was a trend toward reduction in ICU admission in the dupilumab group, all of which implicated dupilumab as a promising treatment for those hospitalized with moderate to severe COVID-19.

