### 6.2 Sample Size justification

Under the protocol HSR 210184, we conducted a randomized double-blind placebo-controlled trial assessing the safety and efficacy of dupilumab for treating hospitalized patients with acute moderate to severe COVID-19, which was designed as an early stage (Phase IIa) and proof of concept study. A total of 40 patients were enrolled from June 23, 2021 through November 180 11, 2021 in the Phase IIa study, and 7 of them died by Day 60. The sample size of 40 in the original Phase II study were determined largely based on the feasibility with a primary goal to collection reliable data and obtain sufficient evidence for future trials. The current proposed study is an extension of the original Phase IIa study under the HSR 210184, to assess the post recovery of remaining 33 patients from COVID-19 with respect to pulmonary function testing (PFT), pulmonary imaging, immune biomarkers and symptoms at one-year follow-up. All data will be collected at a single visit, 1 year (i.e.,  $365 \pm 90$  days) after initial enrollment in the remaining 33 parents from the study HSR 210184. Formal sample size estimation and power analysis is not performed due to the pilot nature of this proposed follow-up study.

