2.0 Outcomes

2.1 Primary outcome: The primary efficacy endpoint of this double-blind, placebo-controlled phase IIa trial is a binary indicator for whether a patient would be alive and free of invasive mechanical ventilation at 28 days. The outcome will be summarized as the proportion of patients alive and free of invasive mechanical ventilation at 28 days in those receiving dupilumab in addition to standard of care (treatment arm) compared to those receiving solely standard of care management (placebo arm).

2.2 Secondary outcomes:

2.2.1 Eosinophilia as the safety outcome: The safety endpoint of this study is a binary indicator for whether a patient would have eosinophilia, which is defined as an absolute eosinophil count $> 0.6 \text{ k}/\mu\text{l}$ at ≥ 1 measurement throughout the study period. The outcome will be summarized as the proportion of patients with eosinophilia for treatment arm and placebo arm respectively. Complete blood counts with differentials

and complete metabolic panels will be measured on Day 0, 2, 5, 7, 14, 28 and 60. Day 7, 28 and 60 optional, although recommended, if patient discharged within the time frame.

2.2.2 **Other secondary safety and efficacy outcomes:**

- Cumulative incidence (defined as number of new events divided by the total number of individuals in the population at risk for the time interval) of grade 3 and 4 adverse events, serious adverse events or death including: injection site reactions, eye/eyelid inflammation, conjunctivitis, oropharyngeal pain, insomnia, tooth ache, gastritis, arthralgia, bacterial pneumonia, herpes viral infection, hypereosinophilic syndrome, hypersensitivity reaction.
- Prevalence of B.1.1.7 and B.1.351 and other SARS-CoV-2 lineages in study cohort: Day 0.
- Plasma total Immunoglobulin E (IgE) levels: Day 0 and 14.
- Plasma inflammatory markers (C-reactive protein and ferritin): Day 0, 7 and 14. Day 7 optional if patient discharged.
- Plasma cytokine levels including TARC (CCL17), YKL40, eotaxin 3 (CCL26), IL-13, IL-4, Arg1, Hyaluronan, soluble ST2: Day 0, 2, 5, 7, 14, and 28. Day 7 and 28 optional if patient discharged.
- Change in PaO₂/SaO₂ to FiO₂ ratio: Day 0, 2, 5, 7 (if patient remains inpatient throughout)
- All-cause mortality rate at 28 days.
- Hospital length of stay (LOS)
- ICU LOS
- Proportion of patients alive and free of invasive respiratory failure at 28 days.
- Proportion of patients alive and free of invasive mechanical ventilation at 60 days.

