5.1 General analysis strategy: The difference between dupilumab and placebo arms in outcome measures will be primarily analyzed under ITT principle, regardless of patient's use of rescue medications, protocol violations, or investigational product discontinuation. The difference will be tested initially with Chi-square for categorical measures (e.g., the primary efficacy endpoint) and two-sample t-test or Wilcoxon rank sum test for continuous measures (e.g., biomarkers). Due to the relatively small sample size in the study, the adjusted treatment effect of dupilumab will be estimated exploratively in the generalized linear regression for the primary and secondary outcomes to account for the potential impact of patient characteristics (e.g., age, sex, race and co-morbidities). Data transformation will be considered for the outcomes with skewed distribution such as hospital length of stay (LOS) and ICU LOS. The trajectory of each immune biomarker over the follow-up time points will be plotted to characterize the change of immune responses over time, and difference in biomarker (or transformed biomarker to improve normal distribution, if necessary) trajectories between the two study arms will be assessed in the mixed effects model.

Since this is intended to be an early stage, proof of concept study for which the primary goal is to inform future trials rather than to perform formal hypothesis testing, no multiplicity adjustment is planned. In addition, machine learning methods such as random forests algorithm will be applied to fully evaluate the treatment effect and predictability of dupilumab and other important predictors on the outcomes non-parametrically.

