- Plasma inflammatory markers (C-reactive protein and ferritin) on Day 0, 7 and 14 (Day 7 would be optional if patient discharged) will be analyzed as longitudinal responses in the linear mixed effects model with Dupilumab treatment as a fixed effect. Since this is a randomized study, significant effect of treatment on intercept is not expected. Thus, the longitudinal analysis will focus on the slope difference between the treatment arms via interaction of treatment and time in the model. Since there are only 3 measures for each subject, only random slopes will be specified as *a priori*. Model fitting indices will be examined carefully to ensure the validity of estimated parameters. If Day 7 data won't be available for all patients, these biomarkers between Day 0 to Day 14 will be analyzed as the IgE above.
- Plasma cytokine levels including TARC (CCL17), YKL40, eotaxin 3 (CCL26), IL-13, IL-4, Arg 1, Hyaluronan, soluble ST2 on Day 0, 2, 5, 7, 14, and 28 (Day 7 and 28 optional if patient discharged) will be analyzed as longitudinal responses

in the linear mixed effects model with Dupilumab treatment as a fixed effect, and with appropriate transformation of biomarkers if necessary. The trajectories of these biomarkers will be carefully evaluated, and the slope difference between the treatment arms will be evaluated by the interaction of treatment and time.

Additional curvature in trajectories will also be explored and captured whenever possible in the linear mixed effects model.

- Change in $\text{PaO}_2/\text{SaO}_2$ to FiO_2 ratio on Day 0, 2, 5, 7 (if patient remains inpatient throughout) will be analyzed as longitudinal responses in the linear mixed effects model, similar methods to that for inflammatory biomarkers and cytokine biomarkers as described above.
- All-cause mortality at 28 days will be analyzed as the binary response, using the same methods as that for the primary efficacy outcome and eosinophilia.
- Hospital length of stay (LOS) and ICU LOS between treatment arms will be analyzed as continuous measures using t-test or Wilcoxon test initially, and adjusted difference and its 95% CI will be estimated from linear regression. Since the distributions of hospital LOS and ICU LOS are often skewed, the log-transformed LOS data will be considered in the analyses.
- The response of being alive and free respiratory failure at 28 days is a binary response and will be analyzed using the same methods as that for the primary efficacy outcome.

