8.0 Missing data

Since patients in this study will be closely followed for mortality and status on mechanical ventilation, the primary outcome of being alive and free of ventilation is likely captured. Dropout from the study will be carefully evaluated for its potential informativeness. A sensitivity analysis will be performed to examine the impact on the proportion and its confidence limits. In particular for the primary endpoint, individuals who withdraw will be considered events if their statuses on day 28 are unknown.

Other outcome variables (clinical conditions and laboratory biomarkers) will have missing data due to dropout from treatment and/or from study participation, or due to missed outpatient visits if patients have been discharged from the hospital. The generalized linear model, or mixed effects model frameworks that will be used for analyses, works with what data are gathered, and assumes missing data are missing at random. For selected secondary outcome analyses, sensitivity analyses will be considered to examine the stability of estimated treatment effects in the face of departures from the assumption of missing at random.

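### Hospital and ICU stay are compared with no rule for in-hospital death, so the direction of the between-arm difference cannot be interpreted

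*SAP*

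**What the plan says.** SAP 2.2.2 lists hospital LOS and ICU LOS as secondary outcomes by name only. It gives no start point, no end point, and no rule for patients who die or who never enter the ICU.

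The analysis is in SAP 5.3.2: "Hospital length of stay (LOS) and ICU LOS between treatment arms will be analyzed as continuous measures using t-test or Wilcoxon test initially". Adjusted differences with 95% CIs then come from linear regression, and because of skewness "the log-transformed LOS data will be considered in the analyses". SAP 5.1 likewise deals only with the shape of the distribution: "Data transformation will be considered for the outcomes with skewed distribution such as hospital length of stay (LOS) and ICU LOS".

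Death is handled elsewhere and separately. In SAP 5.3.2, "All-cause mortality at 28 days will be analyzed as the binary response", and mortality at 60 days and over the first year is analysed as time to event. SAP 8.0 has a rule for unknown status, but for the primary endpoint only: "individuals who withdraw will be considered events if their statuses on day 28 are unknown". For other outcomes it covers dropout and missed visits under missing at random. Death is neither of these.

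On how common death was, Protocol 6.2 says of the 40 enrolled patients that "7 of them died by Day 60". Protocol 3.2 says that "there was reduced 60-day mortality in those who received dupilumab compared to placebo". Neither document gives the split by arm, the dates of death, or the place of death.

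**The concern.** A t-test, rank test or regression on raw days treats fewer days as better, whatever ended the stay. A patient discharged well on Day 4 and a patient who died on Day 4 get the same score. If mortality differs between arms, the LOS contrast carries part of the mortality difference, with a sign that depends on when the deaths occurred.

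Leaving deaths out, the other option open when no rule is set, does not repair this. It conditions on survival, which comes after randomisation, and it departs from the ITT comparison that SAP 3.1 and 5.1 call for.

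The stake is the LOS estimate itself. SAP 5.1 and 7.0 say that the trial is meant to inform future trials and estimate effect sizes. A between-arm LOS difference of unknown direction is a poor input to that.

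There is a smaller, conditional point on scale. If patients never admitted to the ICU are entered as zero ICU days, the logarithm is undefined for them. Logs also give very short stays more weight, and those are the records most affected by early deaths.

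**Working it through.** The plan gives no numerical figure for LOS, so there is nothing to reproduce first. The calculation below shows how far the contrast can move when treatment has no effect on the stay of survivors.

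**From the documents.** 40 patients, 1:1 (SAP 1.4), so 20 per arm; 7 deaths in total (Protocol 6.2); fewer on dupilumab (Protocol 3.2).

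**Assumed, not in the documents.**
- Deaths of 25% v 10%, that is 0.25 × 20 + 0.10 × 20 = 5 + 2 = 7.
- All deaths occur in hospital, and LOS is days to discharge or death.
- Survivor stay is log-normal and the same in both arms: median 8 or 10 days, log-SD 0.6.
- Time to death is log-normal: median m days, log-SD 0.5.

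**Component means.** A log-normal mean is the median × exp(SD²/2).
- Survivors: 8 × exp(0.18) = 9.58 days; 10 × exp(0.18) = 11.97 days.
- Deaths: m × exp(0.125) = 1.133m, giving 3.40, 5.67, 9.07 and 15.86 days for m = 3, 5, 8 and 14.

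**Shift in mean LOS.** Each arm mean is (1 − p) × survivor mean + p × death mean. Hence

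lower-mortality arm minus other arm = (0.25 − 0.10) × (survivor mean − death mean).

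For survivor median 8 and m = 5, the arm means are 0.90 × 9.58 + 0.10 × 5.67 = 9.19 and 0.75 × 9.58 + 0.25 × 5.67 = 8.60. The difference is 0.15 × (9.58 − 5.67) = +0.59 days.

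**Between-trial SD.** The variance of LOS in an arm is (1 − p)V_s + pV_d + p(1 − p)(survivor mean − death mean)², with V = mean² × (exp(SD²) − 1). In the same scenario V_s = 39.75 and V_d = 9.12. The arm variances are 38.07 and 34.96, and the SD of the difference is √((38.07 + 34.96)/20) = 1.91 days.

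| Median time to death | Survivor median 8: shift (SD) | Survivor median 10: shift (SD) |
|---|---|---|
| 3 days | +0.93 (1.97) | +1.29 (2.49) |
| 5 days | +0.59 (1.91) | +0.95 (2.42) |
| 8 days | +0.08 (1.92) | +0.44 (2.38) |
| 14 days | −0.94 (2.25) | −0.58 (2.57) |

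A positive value means that the arm with fewer deaths shows the longer stay. The shift is zero where the two component means are equal, at m = 9.58/1.133 = 8.5 days or 11.97/1.133 = 10.6 days.

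A simulation of the same model agrees. Counting stays only to Day 28 trims the extremes to about +1.2 and −0.85 days. With deaths at a median of 5 days, the lower-mortality arm has the longer mean stay in about 63% to 65% of trials, against 50% by chance. The Wilcoxon test then rejects at the two-sided 5% level in about 7% to 9% of trials.

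**Sensitivity to the split.** With survivor median 8 days, log-SD 0.7 (mean 10.22) and the seven deaths split 3/4, 2/5, 1/6 or 0/7, the same formula gives +0.34, +1.02, +1.71 and +2.39 days for deaths at a median of 3 days. At a median of 15 days it gives −0.34, −1.02, −1.69 and −2.37 days.

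**A death-aware score under the first model.** Hospital-free days to Day 28, with death = 0, favour the lower-mortality arm by about 2.4 to 2.8 days whatever the time of death. Survivor stay is identical here, so all of that difference is mortality. It shows that the sign no longer depends on when deaths occur; it does not show an effect on stay.

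**The case against.** A reader might infer that the LOS comparison is biased against dupilumab, because fewer deaths were reported there. The documents do not support that. They give no death times and no LOS distribution, and only deaths in hospital end a stay. SAP 1.5 excludes patients on invasive ventilation at enrolment, so later deaths are plausible, and those push the other way. Nor does the SAP say that a death counts as a short stay; that follows by default because no rule is set.

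The distortion is also modest. A shift of up to about a day sits against a between-trial SD of about 2 to 2.6 days, and in the 5-day scenarios the rank test rejects little more often than its nominal level.

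LOS is one of many secondary outcomes in a 40-patient proof-of-concept trial without formal confirmatory testing, and it is not an endpoint of the one-year extension protocol. Mortality is reported beside it, and the ordinal scale already ranks death worst. Both limit the risk that a reader is misled, but neither changes the LOS estimate or its confidence interval.

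On the log scale, the SAP only says that transformation will be considered, the Wilcoxon test is available, and SAP 3.1 and 3.2 leave room to adapt. The zero-days problem arises only if patients never in the ICU are included as zeros.

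What stands is the missing rule. With 7 deaths in 40 patients, the comparison as written cannot separate faster recovery from earlier death.

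**Conclusion.** The concern holds as a question of interpretability, not as a bias of known direction. Followed as written, the LOS comparison mixes recovery with death, and the sign of any difference cannot be read. Under the assumed 25% v 10% mortality and identical survivor stay, the shift runs from about +1.3 to −0.9 days (about +1.2 to −0.85 with stays counted to Day 28) as median time to death goes from 3 to 14 days. More extreme splits of the seven deaths give larger shifts in either direction.

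The absence of a rule for death is clear from the text. The size and direction rest on assumed death times, stays and arm split. The plan's own primary endpoint combines survival with freedom from ventilation, so a death-aware measure fits its approach. The change is worth making, at the weight of a secondary outcome.

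**What to change.** Define LOS, including its start point, and state how death enters. Base the between-arm comparison on a death-aware measure: for example, days alive and out of hospital and days alive and out of ICU to Day 28, with death by Day 28 scored 0. Placing deaths at the worst rank would also serve. Compare arms with a Wilcoxon test stratified by the randomisation oxygen stratum (15 L or less v more than 15 L). Give raw LOS descriptively, by arm and survival status. If patients never in the ICU are entered as zero days, do not log-transform ICU days.

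Protocol Section 1.0 reports that parent-trial enrolment closed in November 2021, and results are already described. The new comparison should therefore be reported as a labelled post hoc or sensitivity analysis beside the prespecified one, not in its place.

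The cost is SAP wording and a few lines of code. The planned LOS and mortality analyses already need discharge and death dates. The measure combines survival with stay, so it should be read beside mortality, and it is less familiar than days of stay. It also needs a rule for readmissions, and the documents do not show that readmission dates are collected.

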## APPENDIX:

### NIAID 8-POINT ORDINAL SCALE FOR CLINICAL IMPROVEMENT

- The ordinal scale is an assessment of the clinical status at the first assessment of a given study day. The scale is as follows: 8) Death; 7) Hospitalized, on invasive mechanical ventilation or extracorporeal membrane oxygenation (ECMO); 6) Hospitalized, on non-invasive ventilation or high flow oxygen devices; 5) Hospitalized, requiring supplemental oxygen; 4) Hospitalized, not requiring supplemental oxygen - requiring ongoing medical care (COVID-19 related or otherwise); 3) Hospitalized, not requiring supplemental oxygen - no longer requires ongoing medical care; 2) Not hospitalized, limitation on activities and/or requiring home oxygen; 1) Not hospitalized, no limitations on activities.

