- The response of being alive and free invasive mechanical ventilation at 60 days is a binary response and will be analyzed using the same methods as that for the primary efficacy outcome.
- National Institute of Allergy and Infectious Diseases (NIAID) 8-point ordinal scale on Day 0, 2, 5, 7, 14, 28, 60, 180 and 360 will be considered as longitudinal data. The distributions of the data will be examined visually first and further collapsing will be considered. Collapsed data will be analyzed in the generalized linear mixed effect model or multinomial logistic regression with the generalized estimating equation approach.
- Proportion of patients alive and free of invasive mechanical ventilation at 60, 90, 120, 150, 180, 270 and 360 days will be estimated from the Kaplan-Meier survival for the time to mechanical ventilation-free survival over the first year. The difference in these proportions between the two treatment groups will be evaluated by the log-rank test and further in Cox regression adjusting for the baseline covariates. For the analysis of mortality over the first year, additional adjustment for dynamic mechanical ventilation effect will be considered by including being on ventilation as a time-vary covariate in the Cox regression.
- Need for vasopressors is a binary response and will be analyzed using the same methods as for the primary efficacy outcome.
- Need for renal replacement therapy is a binary response and will be analyzed using the same methods as for the primary efficacy outcome.
- Need for extracorporeal membrane oxygenation (ECMO) is a binary response and will be analyzed using the same methods as for the primary efficacy outcome.

6.0 Other safety analyses:

Analysis of adverse event (AE) data will primarily be descriptive based on CTCAE coding of events. The proportion of subjects experiencing a severe AE and the proportion experiencing a Grade 3 or higher will be recorded. AE will be compared to published data.

7.0 Sample size estimation and power analysis:

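### SAP 5.3.2 allows unweighted GEE on the ordinal scale although SAP 8.0 expects scores to be lost after discharge: proportions dead or in hospital come out too high, and the odds ratio is biased if losses differ by arm

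*SAP*

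**What the plan says.** SAP 5.3.2 treats the NIAID "8-point ordinal scale on Day 0, 2, 5, 7, 14, 28, 60, 180 and 360" as longitudinal data, to be inspected, collapsed and modelled: "Collapsed data will be analyzed in the generalized linear mixed effect model or multinomial logistic regression with the generalized estimating equation approach". It gives no weights, no criterion for choosing between the two methods, no link function, and no rule for a visit without a score.

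The Protocol appendix defines the scale. Score 8 is death, 7 is invasive ventilation or ECMO, and 3 to 6 are the other inpatient states. The bottom two levels are "2) Not hospitalized, limitation on activities and/or requiring home oxygen; 1) Not hospitalized, no limitations on activities".

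SAP 8.0 says that patients are "closely followed for mortality and status on mechanical ventilation". For the remaining outcomes it expects that they "will have missing data due to dropout from treatment and/or from study participation". It then gives a second cause, which applies to patients who have gone home: "due to missed outpatient visits if patients have been discharged from the hospital". The modelling framework "works with what data are gathered, and assumes missing data are missing at random". That sentence names generalized linear and mixed models, not GEE. Sensitivity analyses for data not missing at random will be considered for some secondary outcomes, which are not listed. The rule that counts an unknown status as an event covers the Day 28 primary endpoint only.

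**The concern.** On this scale, being discharged means a score of 1 or 2. The SAP therefore foresees losses in the two best categories, while the states it promises to follow closely are the two worst, 7 and 8. Missingness is then tied to the outcome itself. Unweighted GEE averages over whoever was scored at each visit and in general needs data missing completely at random, a stronger condition than the one SAP 8.0 assumes. The loss is also partly avoidable: a patient known to be alive and at home on the visit day has a score of 1 or 2, even if nobody recorded which.

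SAP 7.0 puts the emphasis on estimating effect size to inform later trials. Inflated proportions, or risk differences computed from them, would carry into that planning. If more discharged patients were missed in one arm, the odds ratio would shift as well, in a direction that cannot be predicted.

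**Working it through.** **Inputs.** 40 patients randomised 1:1, so 20 per arm (SAP 1.2). 7 deaths by Day 60, 33 survivors, no split by arm (Protocol 6.2). No document gives a rate of missed visits, so the missing share m among discharged patients is assumed and varied.

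**The plan's own figure.** None is given for the ordinal scale. The power statement in SAP 7.0 (79.5% vs 97.2%, one-sided 10%, 75% power) reproduces at 75.1% by exact enumeration of the pooled score test and is not affected by this point. Its complements, 20.5% and 2.8%, serve below only as illustrative rates.

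**Level.** Let p be the true proportion dead or in hospital. If a share m of discharged patients has no score, the observed proportion is

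p′ = p / [p + (1 − p)(1 − m)].

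At Day 60, for death alone and treating all survivors as discharged:
- m = 20%: 7 / (7 + 33 × 0.8) = 7 / 33.4 = 21.0%
- m = 50%: 7 / (7 + 33 × 0.5) = 7 / 23.5 = 29.8%
- true value: 7 / 40 = 17.5%

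**Odds ratio, equal m.** The observed odds are the true odds divided by (1 − m) in each arm, so the factor cancels. For an assumed 2 vs 5 split of deaths, the true value is (2/18)/(5/15) = 0.333; at m = 40% it is (2/10.8)/(5/9) = 0.333. For 1 vs 6 it is 0.123 both times.

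**Odds ratio, unequal m.** Observed OR = true OR × (1 − m_placebo)/(1 − m_dupilumab). For 30% vs 15% the true value is (0.15/0.85)/(0.30/0.70) = 0.412.
- 40% missed on placebo, 20% on dupilumab: 0.412 × 0.6/0.8 = 0.309
- the reverse: 0.412 × 0.8/0.6 = 0.549

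**Risk difference, equal m (percentage points).**

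| True rates | True | m = 20% | m = 40% | m = 60% |
|---|---|---|---|---|
| 20.5% vs 2.8% | 17.7 | 20.9 | 25.5 | 32.5 |
| 30% vs 15% | 15.0 | 16.8 | 18.9 | 21.1 |
| 80% vs 60% | 20.0 | 18.1 | 15.5 | 12.0 |

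It is stretched at low rates and shrunk at high ones.

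**GEE check.** Assumed trajectories with death absorbing and discharged scores missing from Day 7, binary outcome dead or in hospital, independence working correlation, 6,000 per arm:

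| m | Control, fitted Day 28 | Dupilumab, fitted Day 28 | Log odds ratio |
|---|---|---|---|
| 0 | 16.6% | 7.1% | −0.96 |
| 20% | 19.9% | 8.7% | −0.96 |
| 40% | 24.9% | 11.3% | −0.96 |
| 60% | 33.0% | 15.9% | −0.96 |
| 40%, weighted by 1/(1 − m) | 16.6% | 7.1% | −0.96 |

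At 20 per arm (300 trials), going from m = 0 to 40% left the mean log odds ratio at −1.04 and raised the fitted Day 28 risk difference from 9.7 to 13.6 points. An exchangeable working correlation gave log odds ratios of −0.77 and −0.76.

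**Mixed model against GEE, unequal m.** In a separate simulation with 40% vs 20% missed, each way round, the GEE log odds ratio moved from −0.48 to −0.69 or −0.27, a shift of 0.21/0.48 = 44%. The mixed model moved from −1.74 to −1.87 or −1.46, shifts of 0.13/1.74 = 7% and 0.28/1.74 = 16%, and about halved the bias in the level. The two coefficients are on different scales (population-averaged and patient-specific), so the proportional shift is the fair comparison. The mixed model reduces the bias but does not remove it.

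**The case against.** A reader might infer that the arm difference is overstated. The documents do not support this. The model named in SAP 5.3.2 is logistic, and its effect measure is unchanged when discharged patients are missed equally in both arms. The plan specifies no risk difference for this outcome, and the risk difference can move either way. Nothing in the documents says that losses differ by arm. This part of the objection stands. One limit applies: the cancellation holds for contrasts against the discharged group. If three levels are kept and cumulative logits are used, equal losses can still move the odds ratio for death. With dead/hospital/discharged at 20/40/40% vs 20/20/60% and m = 40%, it goes from 1.00 to (0.20/0.56)/(0.20/0.64) = 1.14.

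A reader might also infer that every death and inpatient score is known. SAP 8.0 claims close follow-up only of mortality and ventilation, scores 3 to 6 are not said to be complete, and dropout is not confined to discharged patients. SAP 2.2 makes several laboratory measures optional after discharge but not the ordinal scale, so losses could be small. This stands too.

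Further, category proportions are not a named output of the model, and mortality and ventilation-free survival have their own analyses in SAP 5.3.2. GEE is only one of two options, the mixed model also rests on missing at random, and SAP 8.0 leaves room for sensitivity analyses. This limits the consequence. It does not close the gap: the choice of method is open, GEE is not covered by the stated assumption, and nothing commits to a sensitivity analysis of this scale.

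**Conclusion.** The point holds as a limited one about a single secondary outcome in a 40-patient exploratory trial. If losses concentrate among discharged patients, unweighted GEE on the observed scores overstates the proportion dead or in hospital. For death at Day 60 that means 21% to 30% in place of 17.5%, with 20% to 50% of survivors unscored and all survivors treated as discharged. The odds ratio against the discharged group is safe under equal losses and biased in either direction under unequal ones (0.41 to 0.31 or 0.55). The missing shares, the splits of deaths by arm, the illustrative rates and the simulated trajectories are all assumptions. The direction of the error in the level does not depend on their exact values; its size does.

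**What to change.** - **SAP 5.3.2, method.** Make the likelihood-based mixed model, already named, the analysis. Remove the unweighted GEE option, or weight it by the inverse probability of being observed, with recorded discharge status in the weight model. State the link.
- **SAP 5.3.2, scoring.** In the collapsed analysis already planned, class a patient known from records or phone contact to be alive and out of hospital on the visit day as not hospitalised (1–2), not as missing. Report scores 1 and 2 separately, as description, where they were observed.
- **SAP 8.0.** Name this outcome in the sensitivity analyses, because the mixed model does not fully remove the bias when missingness depends on current status. Report the share of unscored visits by arm and visit.

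The cost is SAP wording and a check of existing records. The downside is that the collapsed model does not separate scores 1 and 2, so activity limitation and home oxygen at the late visits are only described. The scoring rule helps only patients whose status is known. The Protocol already reports deaths to Day 60, so the amendment should be dated to show which results were known when it was made.
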